Appendix - Critical Care Family Needs Inventory (CCFNI) questionnaire

1. *Do you feel that the best possible care is being given to the patient?*
1. Almost all of the time 2. Most of the time 3. Only some of the time 4. None of the time
2. *Do you feel that the hospital personnel care about the patient?*
1. Almost all of the time 2. Most of the time 3. Only some of the time 4. None of the time
3. *Have the explanations given to you about the patient's condition been in terms that you can understand?*
1. Almost all of the time 2. Most of the time 3. Only some of the time 4. None of the time
4. *Do you feel that you have been given honest information about the patient's condition and progress?*
1. Almost all of the time 2. Most of the time 3. Only some of the time 4. None of the time
5. *Do you understand what is happening to the patient and why things are being done?*
1. Almost all of the time 2. Most of the time 3. Only some of the time 4. None of the time
6. *Have the staff members been courteous to you?*
1. Almost all of the time 2. Most of the time 3. Only some of the time 4. None of the time
7. *Have any of the staff members shown interest in how you are doing?*
1. Almost all of the time 2. Most of the time 3. Only some of the time 4. None of the time
8. *Do you believe that someone will call you at home with any major or significant change in the patient's condition?*
1. Almost all of the time 2. Most of the time 3. Only some of the time 4. None of the time
9. *Have the hospital personnel explained the equipment being used?*
1. Almost all of the time 2. Most of the time 3. Only some of the time 4. None of the time
10. *I am very satisfied with the medical care the patient receives.*
1. Almost all of the time 2. Most of the time 3. Only some of the time 4. None of the time
11. *There are some things about the medical care the patient receives that could be better.*
1. Almost all of the time 2. Most of the time 3. Only some of the time 4. None of the time
12. *Do you feel comfortable visiting with the patient in the intensive care unit?*
1. Almost all of the time 2. Most of the time 3. Only some of the time 4. None of the time
13. *Is the waiting room comfortable?*
1. Almost all of the time 2. Most of the time 3. Only some of the time 4. None of the time
14. *Do you feel alone and isolated in the waiting area?*
1. Almost all of the time 2. Most of the time 3. Only some of the time 4. None of the time

Hospital Anxiety and Depression Scale (HADS),

**Tick the box beside the reply that is closest to how you have been feeling in the past week.
Don't take too long over you replies: your immediate is best.**

D	A		D	A	
	I feel tense or 'wound up':			I feel as if I am slowed down:	
3	Most of the time	3		Nearly all the time	
2	A lot of the time	2		Very often	
1	From time to time, occasionally	1		Sometimes	
0	Not at all	0		Not at all	
	I still enjoy the things I used to enjoy:			I get a sort of frightened feeling like 'butterflies' in the stomach:	
0	Definitely as much	0		Not at all	
1	Not quite so much	1		Occasionally	
2	Only a little	2		Quite Often	
3	Hardly at all	3		Very Often	
	I get a sort of frightened feeling as if something awful is about to happen:			I have lost interest in my appearance:	
3	Very definitely and quite badly	3		Definitely	
2	Yes, but not too badly	2		I don't take as much care as I should	
1	A little, but it doesn't worry me	1		I may not take quite as much care	
0	Not at all	0		I take just as much care as ever	
	I can laugh and see the funny side of things:			I feel restless as I have to be on the move:	
0	As much as I always could	3		Very much indeed	
1	Not quite so much now	2		Quite a lot	
2	Definitely not so much now	1		Not very much	
3	Not at all	0		Not at all	
	Worrying thoughts go through my mind:			I look forward with enjoyment to things:	
3	A great deal of the time	0		As much as I ever did	
2	A lot of the time	1		Rather less than I used to	
1	From time to time, but not too often	2		Definitely less than I used to	
0	Only occasionally	3		Hardly at all	
	I feel cheerful:			I get sudden feelings of panic:	
3	Not at all	3		Very often indeed	
2	Not often	2		Quite often	
1	Sometimes	1		Not very often	
0	Most of the time	0		Not at all	
	I can sit at ease and feel relaxed:			I can enjoy a good book or radio or TV program:	
0	Definitely	0		Often	
1	Usually	1		Sometimes	
2	Not Often	2		Not often	
3	Not at all	3		Very seldom	

Please check you have answered all the questions

Scoring:

Total score: Depression (D) _____ Anxiety (A) _____

0-7 = Normal

8-10 = Borderline abnormal (borderline case)

11-21 = Abnormal (case)

Impact of Events Scale Revised (IES-R) questionnaire

INSTRUCTIONS: Below is a list of difficulties people sometimes have after stressful life events. Please read each item, and then indicate how distressing each difficulty has been for you DURING THE PAST SEVEN DAYS with respect to _____ (event)

that occurred on _____ (date). How much have you been distressed or bothered by these difficulties?

	Not at all	A little bit	Moderately	Quite a bit	Extremely
1. Any reminder brought back feelings about it	0	1	2	3	4
2. I had trouble staying asleep	0	1	2	3	4
3. Other things kept making me think about it.	0	1	2	3	4
4. I felt irritable and angry	0	1	2	3	4
5. I avoided letting myself get upset when I thought about it or was reminded of it	0	1	2	3	4
6. I thought about it when I didn't mean to	0	1	2	3	4
7. I felt as if it hadn't happened or wasn't real.	0	1	2	3	4
8. I stayed away from reminders of it.	0	1	2	3	4
9. Pictures about it popped into my mind.	0	1	2	3	4
10. I was jumpy and easily startled.	0	1	2	3	4
11. I tried not to think about it.	0	1	2	3	4
12. I was aware that I still had a lot of feelings about it, but I didn't deal with them.	0	1	2	3	4
13. My feelings about it were kind of numb.	0	1	2	3	4
14. I found myself acting or feeling like I was back at that time.	0	1	2	3	4
15. I had trouble falling asleep.	0	1	2	3	4
16. I had waves of strong feelings about it.	0	1	2	3	4
17. I tried to remove it from my memory.	0	1	2	3	4
18. I had trouble concentrating.	0	1	2	3	4
19. Reminders of it caused me to have physical reactions, such as sweating, trouble breathing, nausea, or a pounding heart.	0	1	2	3	4
20. I had dreams about it.	0	1	2	3	4
21. I felt watchful and on-guard.	0	1	2	3	4
22. I tried not to talk about it.	0	1	2	3	4

INTERVIEW GUIDE

Prepping for the interview

- **Review the above information**
- **Adopt an empathic stance.** Use open-ended questions to elicit large themes. Clarifying and close-ended questions can be used to narrow themes. Use reflective statements, and paraphrasing to let the participant know you're listening. Use your tone of voice to convey interest and empathy.

The Interview

- Ask for consent to record the interview to aid in note taking.
- Introduce yourself, and remind participants that this stage of the study involves an interview. Encourage participants to be open and forthcoming, and remind them that the information they provide may be useful for supporting other surrogates in the future.
- Tell the participant that the interview focuses on his/her experience during two periods – 1) while his/her loved one was hospitalized at Rush and 2) the time since his/her loved one was hospitalized at Rush.

(The questions are organized to elicit general observations, negative aspects of the ICU experience, and then to elicit positives. This order was chosen for two-reasons. First, to end the interview on a more “positive” tone. Second, to prompt participants to home in on aspects that could be addressed on the coaching intervention phase of the study)

Questions about your ICU experience

- What are your thoughts about your experience with the ICU?
- What are your thoughts about the ways the COVID-19 pandemic affected your experience in the ICU?
- What about your ICU experience was difficult?
 - Were there aspects of ICU care i.e lack of visitation, issues with communication?
Were there external factors i.e job loss, family situation?
 - Did you have added responsibilities to other family members while your loved one was in the ICU
- What was most useful for coping?
- Refer to survey responses during ICU stay that stood out, ask to elaborate

Questions about your post-ICU experience

- Tell me how life has been after ICU discharge (note if the patient is alive or not)
- What are your thoughts about the ways the COVID-19 pandemic affected your experience *after* ICU discharge.
- What about your experience has been difficult after ICU discharge?
 - When asking this question, review whether the patient is now at home and/or is having ongoing symptoms
 - Have you had added responsibilities to other family members since your loved one was in the ICU
- What has been most useful for coping?

- When asking this question, review whether the subject has sought out help from a mental health provider
- When asking this question, review whether the subject was in the daily email update group or control group. Has the subject referenced the summaries after ICU discharge?
- Refer to survey responses *after* ICU stay that stood out, ask to elaborate
- Going forward, what resources would help you or others in similar situations recover from your experience with the ICU?

Assess interest in a support intervention.

- Refer to whether the subject has sought out help from a mental health provider
 - Has this been helpful? Why or why not
- Refer to the subject's impression of the helpfulness of mental health.
 - Why might it be helpful or unhelpful
- Use the subject's responses to the *whole* interview to suggest possible types of support interventions and gauge the subject's interest (we are expecting about half of the subjects who complete this interview to complete the support intervention)

Thank the participant for their participation. Is there anything else you would like us to know?

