For the last year, my research group has been enrolling families in a clinical trial evaluating the impact of providing them with daily written summaries of ICU rounds on their experience (NCT03969810). Using validated instruments, we have measured symptoms of anxiety, depression, and acute stress among family members at multiple time points during the ICU stay. During the hospitalization, families also participated in interviews dealing with their experiences. Compared to the 96 family members who were enrolled prior to the COVID-19 pandemic, the 88 family members who have been enrolled during the COVID-19 pandemic were more likely to develop clinically significant depressive symptoms (27% vs. 13%, p=0.03 for difference) and tended to develop clinically significant acute stress symptoms (61% vs 48%, p=0.11 for difference). There were similar levels of clinically significant symptoms of anxiety before and during the COVID-19 pandemic (42% vs. 35%, p=0.43 for difference) (manuscript in preparation). It is likely that restrictions on family visitation and challenges with communication during the COVID-19 pandemic contributed to the high psychological symptom burden among family members during this time period.

The best practices for clinicians to engage with family members in times when they cannot visit their loved ones in the ICU are poorly understood. It is unclear the degree to which families of

COVID-19 patients continue to have psychological symptoms after the patient is discharged and how these symptoms may be impacting quality of life and the patient's recovery. For family members who develop mental health disorders, it is likely that many do not seek out professional help. To address these gaps in knowledge, we propose the following three specific aims.

- 1. To determine the extent to which families of COVID-19 patients have psychological symptoms 3-6 months after the patient was discharged from the hospital.** We will reconsent family members who participated in our initial study during the COVID-19 pandemic. We will conduct one phone interview and use validated instruments to determine the prevalence of anxiety, depression, and post-traumatic stress disorder.

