- 2. To determine the characteristics of ICU care delivery during the COVID-19 pandemic that were associated with the development of psychological symptoms among families.** To achieve this goal, we analyze phone interviews conducted during and after the hospitalization. We compare themes among families who developed psychological symptoms to those who did not.
- 3. To determine whether a trauma-focused cognitive behavioral therapy intervention helps reduce the burden of symptoms among family members with psychological symptoms.** We will pilot a program in which family members with clinically significant psychological symptoms will be offered up to six phone/video counseling sessions with mental health professionals. To determine the effect of this therapy, we will conduct phone interviews and use validated instruments to determine the prevalence of anxiety, depression, and post-traumatic stress disorder after the intervention.

Methods

Enrollment

Surrogates of ICU patients with COVID-19 who were enrolled in the study "ICU Rounding Summaries for Families of Critically Ill Patients" (19042604-IRB01) will be approached to participate in a follow-up study dealing with their mental health after patient discharge. We will email and call surrogates to describe the project and provide an informed consent form for them to review.

Inclusion criteria

- The patient's surrogate was enrolled in "ICU Rounding Summaries for Families of Critically Ill Patients" (19042604-IRB01) and the patient had COVID-19
- The patient has been discharged from the hospital

Exclusion criteria

- None

Intervention

Part 1- Post-ICU discharge survey and Interview

Upon enrollment in this post-ICU discharge follow-up study, the subject (surrogate of the ICU patient) will complete a survey dealing with the patient's course since Rush discharge

1. Is the patient still alive?

- a. If deceased, did the patient pass away at Rush or after discharge from Rush?
- b. If alive, is the patient at home?
 - i. If at home, for how long? Is he/she receiving home health services?
- 2. If the patient did not pass away at Rush, did the patient spend time in a rehabilitation hospital, nursing home, or long-term acute care hospital after discharge from Rush?
- 3. Is the patient currently having any of the following symptoms (check all that apply).
 - a. Fatigue
 - b. Trouble Breathing
 - c. Difficulty speaking
 - d. Difficulty eating
 - e. Difficulty thinking or paying attention

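### CCFNI items 12-14 offer no not-applicable choice and the form names no period or setting, so on the form alone some post-discharge answers cannot be told apart from real ICU ratings (minor; one descriptive Part 1 measure)

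*Combined protocol and SAP*

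**What the plan says.** The Outcomes section lists the CCFNI under Part 1 as 14 questions, each scored 1 to 4. The inclusion criteria place its completion after the hospital stay: "The patient has been discharged from the hospital". Aim 1 sets follow-up at 3 to 6 months after discharge.

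The appendix form gives every item the same four frequency choices. The last three items are:

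- item 12: "Do you feel comfortable visiting with the patient in the intensive care unit"
- item 13: "Is the waiting room comfortable"
- item 14: "Do you feel alone and isolated in the waiting area"

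No item has a not-applicable choice, and the form carries no instruction on period or setting. Several care items are in the present tense, for example item 1: "Do you feel that the best possible care is being given to the patient".

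The opening section says that "restrictions on family visitation and challenges with communication during the COVID-19 pandemic" probably added to the families' symptom burden. The Part 1 survey asks "did the patient spend time in a rehabilitation hospital, nursing home, or long-term acute care hospital after discharge from Rush". It also asks whether a patient at home receives home health services, and whether a deceased patient died at Rush or later.

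Under Statistical Analysis, opinions on ICU care are to be read from the surveys and the recorded interviews together.

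**The concern.** Items 12-14 presuppose that the surrogate visited the ICU or used its waiting area. In this cohort that cannot be assumed. A surrogate who did neither must leave the item blank or pick a frequency that describes nothing, and the plan has no rule for either case. If such respondents pick the lowest frequency, items 12 and 13 look worse than the truth, while item 14, which is worded negatively, looks better. The error therefore has no consistent direction across the three items.

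The second difficulty is the period rated. Months after discharge, a present-tense item that names no setting, such as 1, 5, 10 or 11, could be answered about a later facility or about home health care. The HADS and IES-R forms in the same appendix state their time frames (the past week and the past seven days). The CCFNI form does not.

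What is at stake is the description of families' views of ICU care, for which the CCFNI is one of two sources. The covariates listed under Outcomes (death, time since discharge, own use of mental health services, receipt of written summaries) include neither visiting nor waiting-area use, so the planned analysis would not separate these answers.

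**Working it through.** **1. The plan's own figure.** The appendix form has 14 items with four choices each. This matches the Outcomes section.

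**2. Items that may not apply.** Items 12, 13 and 14: 3/14 = 21.4% of the form.

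**3. Largest possible distortion of an item's response share.** Let

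- t = the true share giving a certain response among those to whom the item applies,
- r = the share giving that response among those to whom it does not apply but who answered anyway,
- f = the fraction of recorded answers that come from the second group.

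Reported share = (1 - f)t + f r, so the error is f(r - t). Since r and t lie between 0 and 1, its size is at most f. The bound is reached only if one group gives the response always and the other never. If all those to whom the item does not apply leave it blank, f = 0 and there is no error.

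**4. Numbers put in.** The Statistical Analysis section expects about 70 Part 1 completers. The documents do not say how many did not visit or did not use a waiting area, so the values of f below are assumptions. All 70 are taken to answer. The last column is the 95% half-width for a share of 50% among those left, 1.96 × sqrt(0.25/n). This is a normal approximation and is rough at n = 14.

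| f (assumed) | Inapplicable answers | Error at most (points) | n left, 70(1 - f) | Half-width (points) |
|---|---|---|---|---|
| 0 | 0 | 0 | 70 | 11.7 |
| 10% | 7 | 10 | 63 | 12.3 |
| 20% | 14 | 20 | 56 | 13.1 |
| 30% | 21 | 30 | 49 | 14.0 |
| 50% | 35 | 50 | 35 | 16.6 |
| 80% | 56 | 80 | 14 | 26.2 |

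The third column bounds the error if nothing is changed. The last shows the precision left if the items are reported only among those to whom they apply.

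**5. Period and setting.** No arithmetic applies. The Part 1 survey separates patients at home with or without home health services, patients who spent time in another facility, and patients who died at Rush or after leaving it. In each of these situations except death at Rush there may be later care to rate, and nothing on the CCFNI form rules out rating it. The documents give no numbers for these groups.

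**The case against.** The strongest reply is that the form is not read in isolation. Every Part 1 subject is to be interviewed by a psychologist who reviews the survey answers and asks follow-up questions. The interview guide separates the hospital stay from the time since, allows clarifying and closed questions, prompts on the absence of visits, and tells the interviewer to ask about post-ICU survey answers that were notable. A puzzling answer to item 12 could well be explained there. This stands as partial mitigation, and it limits the claim to the form alone. It does not remove the problem. The prompt reaches only answers that strike the interviewer, the guide never mentions the waiting area, and nothing says that an explanation alters the recorded item.

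A second reply is that little depends on the CCFNI. The plan specifies no total, cut-off or test for it, and does not commit to publishing item response shares. Aim 2 rests on interviews: "we analyze phone interviews conducted during and after the hospitalization". That is right, and it is why the point is minor.

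A third is that the form's title refers to critical care and item 2 names hospital personnel, so many respondents will think of the ICU anyway. That is plausible, but the form does not secure it.

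A reader might infer more than the documents support:

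- *That a fixed proportion of the care items is compromised.* How many items are open to a later-care reading is a matter of judgement. Items 3, 4, 6 and 7 also name no setting, while item 2 does. Items 1, 5, 10 and 11 are examples, not a count.
- *That a later-care reading is possible only for a living patient now in another facility.* The survey itself provides for home health services and for death after discharge from Rush.
- *That most surrogates never visited.* The documents report restrictions but give no number.

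**Conclusion.** The point holds as a minor one. As written, the plan would record some inapplicable answers to items 12-14, and possibly some ratings of later care, as ratings of the ICU, and the form alone would not show which. The distortion in an item's response share is at most f, which is unknown: 10 points at 7 of 70 and 30 points at 21 of 70 are ceilings under assumed values, not estimates.

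The conclusion rests on two assumptions: that the appendix shows the whole form, and that at least some surrogates did not visit or did not use the waiting area. The first is supported by the fact that the HADS and IES-R instructions are shown in the same appendix. The second is likely given the stated restrictions, but is not quantified.

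It would be wrong to conclude that the trial's symptom results are in doubt. HADS and IES-R state their own time frames, Part 2 compares only those two instruments, and its paired t-test does not use the CCFNI.

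**What to change.** 1. Add a lead-in to the CCFNI: *Please answer all questions about the time the patient was in the ICU at Rush, even where the wording is in the present or future tense.* The last clause is needed because items such as 1 and 8 would otherwise still clash with a past period.
2. Add *Not applicable - I did not visit* to item 12 and *Not applicable - I did not use the waiting area* to items 13 and 14.
3. Report items 12-14 separately among those to whom they apply, with that number shown.
4. Add one interview prompt: *Did you visit the patient in the ICU, and did you use the waiting area?*
5. For forms already collected, use the interview to define the denominator. Where it does not settle the matter, count the answer as *applicability not known* and show how many there are.

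The cost is a one-page form edit, one prompt and one reporting sentence. The Part 1 section already foresees a protocol amendment after the first 10 subjects, and if that is still to come the change could go with it. There are two downsides: slightly less comparability with any data collected on the unmodified form, and smaller denominators for three items, with the loss of precision shown in the last column of the table.
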